#### 8.2.1 Ascorbic Acid Dose Modification

One dose modification of ascorbic acid is allowed to 0.75 g/kg (if two dose reductions are required, the patient will go off protocol treatment).

Ascorbic acid dose modifications for symptoms other than grade 3 or 4 toxicities should be discussed with and approved by the Protocol Chair.

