# 1.0 SCHEMA

Total Number of Patients: 15

Olaparib is taken 300 mg BID orally

Ascorbate is given 1 g/kg, 2 times per week intravenously (first three doses [over 1.5 weeks]: titrate 0.25 g/kg, 0.5 g/kg, and 0.75 g/kg. Starting with cycle 1 week 2, the dose of Ascorbate will be 1 g/kg as long as this dose is tolerated)

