# 7.6.2 Ascorbic Acid Administration

For the first cycle, on cycle 1 day 8, collect blood for CTCs and then start Ascorbic Acid. The first three doses of ascorbic acid will be titrated as such: 0.25~g/kg, 0.5~g/kg, 0.75~g/kg in 1000ml of sterile water (not to exceed 500 mL per hour). If tolerated, the subsequent doses will be 1 g/kg. Infusions will be twice a week, and should not be less than 24 hours apart. It is recommended that ascorbic acid be given through a port due to frequency of infusion, but a port is not required.

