# 8.0 DOSING DELAYS/MODIFICATIONS

# 8.1 Dosing Delays

All scheduled cycles occur over a 28-day period. If necessary, treatment may be delayed for up to 4 weeks. If treatment is delayed more than two weeks, the Principal Investigator must be contacted for further instructions on continued treatment. Additional delays or modifications to the treatment schedule must be approved by the Protocol Chair. When the delay is due to toxicity, then the next cycle may begin with a dose reduction.

Ascorbic acid will be withheld for the following drug-related toxicities:

- $Cr \ge 1.6 \times ULN$  (for patients with  $Cr \ge 1.6 \times ULN$ , calculated or measured creatinine clearance must be  $\ge 50 \text{ mL/minute}$  (Cockcroft-Gault))
- Common Terminology Criteria for Adverse Events (CTCAE) Grade 3 or 4 non-hematologic toxicity excluding asymptomatic electrolyte aberrations
- Any AE, laboratory abnormality, or intercurrent illness that, in the judgement of the investigator, warrants delaying the dose of study medication

Olaparib will be withheld for the following drug-related toxicities:

Absolute neutrophil count
 Platelets
 Hemoglobin
 Total bilirubin
 AST (SGOT)/ALT(SGPT)
 ≤ 750/ mm³, see Table 8
 ≤ 8 hgb, If < 10, see Table 7

 ≥ 1.5XULN
 ≥ 2.5 x ULN (<5x ULN if with known liver m

• AST (SGOT)/ALT(SGPT)  $\geq 2.5 \text{ x ULN (<}5\text{x ULN if with known liver metastases}$  provided bilirubin is normal)

- Common Terminology Criteria for Adverse Events (CTCAE) Grade 3 or 4 non-hematologic toxicity excluding asymptomatic electrolyte aberrations
- Any AE, laboratory abnormality, or intercurrent illness that, in the judgement of the investigator, warrants delaying the dose of study medication

If dosing parameters for Ascorbic Acid are not met, study participants may continue with olaparib therapy. If dosing parameters for olaparib or are not met, study participants may continue with Ascorbic Acid therapy. Dose interruptions are allowed as required, for a maximum of 4 weeks. Patients who require an interruption in olaparib or ascorbic acid for >4 weeks due to toxicity must permanently discontinue study drug unless an exemption is granted by the protocol chair (Refer to section 13.6 for stopping rule). Where toxicity reoccurs following re-challenge with study treatment, then the patient should be considered for dose reduction or must permanently discontinue study treatment per investigator judgement.

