#### 8.2 Dose Modifications

Patients enrolled in this study will be evaluated clinically and with standard laboratory tests before and at regular intervals during their participation in this study as specified in **Section 7.3.1.** The NCI CTCAE v.5.0 will be used to grade adverse events.

At each study visit for the duration of their participation in the study, patients will be evaluated for adverse events (all grades), serious adverse events (SAEs), and adverse events that require study drug interruption or discontinuation.

Adverse events possibly related to either study drug must be resolved to grade 1 or baseline prior to resumption of dosing.

Patients who experience grade 3 of 4 toxicities (individually defined in **Section 8.1**) that are eligible for retreatment will be dose reduced. After a two-week dose delay, if the grade 3 or 4 toxicity resolves to grades 0-2 (grade 2 peripheral neuropathy must resolve to grade 1 if interfering with instrumental ADL), then the following dose reductions are to be applied.

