Report AEs to the Protocol Chair and CRO within 24 hours once identified as an unacceptable toxicity (defined in Section 8.1).

Report Olaparib AESIs to Lead Study Coordinator, Protocol Chair, and AstraZeneca within 24 hours once identified (defined in Section 9.1.3) using the form found in Appendix F.

[name] (Protocol Chair): [contact]

[name] (Monitor): [contact]

AstraZeneca: [contact]

[contact]

All SAEs (including death) occurring from the first dose study drug, throughout the study, and 30 days after the last dose of study drug or before initiation of a new antineoplastic treatment (whichever comes first) must be reported. All SAEs that the investigator considers related to the study drug occurring after the follow-up periods must be reported.

SAEs will be reported promptly to the Protocol Chair, AstraZeneca, and McGuff within 24 hours of recognition of the adverse event using the form found in **Appendix B**. If this falls on a weekend or holiday, an email notification is acceptable but must be followed by an SAE reporting form on the next business day.

SAE reports and any other relevant safety information are to be sent to:

[name] (Monitor): [contact]

[name] (Protocol Chair): [contact]

AstraZeneca: [contact]

[contact]

McGuff: [contact]

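### The only reduced ascorbate dose in Section 8.2.1, 0.75 g/kg, is not a reduction after an event during titration or, on actual weight, from 133.3 kg upward

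*Combined protocol and SAP*

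**What the plan says.** Section 8.2 states that patients with grade 3 or 4 toxicity "that are eligible for retreatment will be dose reduced" and, once the toxicity has resolved sufficiently, "then the following dose reductions are to be applied". Section 8.1 is softer: "When the delay is due to toxicity, then the next cycle may begin with a dose reduction".

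For ascorbate, the reductions that follow consist of one level in Section 8.2.1: "One dose modification of ascorbic acid is allowed to 0.75 g/kg (if two dose reductions are required, the patient will go off protocol treatment". The same section sends other ascorbate modifications to the Protocol Chair, but only those for symptoms other than grade 3 or 4 toxicities.

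Two other parts of the regimen bear on this level:

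- **Titration.** Section 7.6.2: "The first three doses of ascorbic acid will be titrated as such", with doses of 0.25, 0.5 and 0.75 g/kg. The schema moves patients to 1 g/kg "as long as this dose is tolerated".
- **Cap.** Table 2 (footnote 2) and Section 7.10 limit the dose to 100 g for patients over 100 kg. Section 8.2.1 does not say whether 0.75 g/kg is taken on actual weight or scaled from the capped dose.

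**The concern.** A dose-reduction rule should give a dose lower than the one that preceded the event. Section 8.2.1 seems to assume that the patient was on an uncapped 1 g/kg. If the event comes during titration, or if the patient is well over 100 kg and the pharmacy works from actual weight, the single named level may not be lower.

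Olaparib does not share this problem. Table 4 steps from 300 mg to 250 mg to 200 mg twice daily, and each step is below the last.

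At stake is the safety of a few patients and uniform dosing across sites in a multi-center study. Section 4.2.8 says there are no clinical data on this combination in castration-resistant disease, so the restart dose after a severe early event should be written down.

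**Working it through.** **Inputs.** Titration doses 0.25, 0.5 and 0.75 g/kg (Schema; Section 7.6.2). Full dose 1 g/kg, at most 100 g above 100 kg (Table 2, footnote 2; Section 7.10). Reduced dose 0.75 g/kg (Section 8.2.1).

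**The plan's own figures.** Table 2 gives a 75 kg example. 75 × 0.25 = 18.75 g; 75 × 0.5 = 37.5 g; 75 × 0.75 = 56.25 g; 75 × 1 = 75 g. All four agree with the footnote. No figure in the protocol is miscalculated.

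**Titration.** Reduced level divided by the dose at the event:

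| Dose at event (g/kg) | 0.75 ÷ dose | Change |
|---|---|---|
| 0.25 (first infusion) | 3.0 | +200% |
| 0.5 (second) | 1.5 | +50% |
| 0.75 (third) | 1.0 | 0% |
| 1.0 (full dose, up to 100 kg) | 0.75 | −25% |

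The named level is below none of the three titration doses. After the third infusion it is 25% below the next planned dose, but equal to the dose at which the event occurred.

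**Cap.** Above 100 kg the full dose is 100 g. On actual weight W the reduced dose is min(0.75 × W, 100) g. Scaled from the cap it is 0.75 × 100 = 75 g. The cut is 1 − reduced dose ÷ 100.

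| Weight (kg) | Actual-weight dose (g) | Cut | Capped-reading dose (g) | Cut | Difference (g) |
|---|---|---|---|---|---|
| 100 | 75 | 25% | 75 | 25% | 0 |
| 110 | 82.5 | 17.5% | 75 | 25% | 7.5 |
| 120 | 90 | 10% | 75 | 25% | 15 |
| 130 | 97.5 | 2.5% | 75 | 25% | 22.5 |
| 133.3 or more | 100 | 0% | 75 | 25% | 25 |

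Break-even weight: 0.75 × W = 100, so W = 100 ÷ 0.75 = 133.3 kg.

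**Does another clause supply the missing dose?**

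- The tolerance condition in the Schema and Section 7.6.2 governs whether to advance. It gives no restart dose.
- Section 8.1 withholds ascorbate for drug-related grade 3 or 4 non-hematologic toxicity, apart from asymptomatic electrolyte changes, and lets olaparib continue. It says when to hold, not what dose to resume.
- Section 8.1 also requires contact with the Principal Investigator after a delay of more than two weeks, and adds: "Additional delays or modifications to the treatment schedule must be approved by the Protocol Chair". Neither provision states a dose.
- Section 9.5.1 requires notification: "Report AEs to the Protocol Chair and CRO within 24 hours once identified as an unacceptable toxicity (defined in Section 8.1". That informs the Chair but sets no dose.
- The Chair clause in Section 8.2.1 leaves out grade 3-4 events, which are the ones at issue.

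**The case against.** The strongest reply is that Section 8.2.1 is meant as a step down from the 1 g/kg goal, and that titration has its own control because a patient with a severe event has not tolerated the dose and does not advance. Much of this stands. A reader might infer that the protocol directs a tripling of the dose after a grade 3-4 event at 0.25 g/kg. The documents do not support that: Section 8.2 calls for a reduction, advancing depends on tolerance, ascorbate is withheld for such non-hematologic events, and Section 7.4 lets the investigator stop treatment. What remains is that no lower level is named for a patient who recovers and is restarted.

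A reader might also treat any cut smaller than 25% as a breach. It is not one. Section 8.2 promises a reduction, not a percentage, and 82.5, 90 and 97.5 g are all below 100 g. On actual weight the rule fails outright only from 133.3 kg. Below that, the fault is the unstated weight basis.

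Section 8.2.1 can further be read as a floor, so that anyone needing less than 0.75 g/kg leaves protocol treatment. That is plausible but unwritten, and its wording about a second reduction does not describe a first event at 0.25 or 0.5 g/kg.

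Finally, the affected group is likely to be small. Titration is three infusions over about 1.5 weeks, and Section 4.2.7 cites a dose-escalation study with no toxicity above 1.5 g/kg. This limits the size of the point and supports a minor rating. It does not supply the missing dose.

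**Conclusion.** The defect is real and minor. The one ascorbate reduction in Section 8.2.1 does not lower the dose after an event at any of the three titration infusions. On the actual-weight reading it does not lower the dose at 133.3 kg or more either. Between 100 and 133.3 kg it is a valid but shrinking reduction, and the two readings of the same sentence differ by up to 25 g.

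The titration part applies only if ascorbate is the drug being reduced (Section 8.2 does not say which), the patient recovers, and ascorbate is restarted. The cap part also depends on a site using actual weight. The documents give neither the expected rate of grade 3-4 toxicity during titration nor the share of patients over 100 kg, so the number affected cannot be estimated; in a trial of at most 15 it is likely to be small. No effect on the sample size or the PSA50 analysis is claimed.

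**What to change.** Amend Section 8.2.1 in three short steps:

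1. Give the reduced dose as 0.75 g/kg, maximum 75 g. The cut is then 25% of the full dose at every weight.
2. Add that after a grade 3-4 toxicity attributed to ascorbate, any restart must be below the dose at which the event occurred. The 0.75 g/kg level then applies only to events at the full dose, and a patient with an event during titration does not restart at or above that dose. If the sponsor wants to allow a lower restart, it should name the level, for example the preceding tolerated step. After an event at 0.25 g/kg there is no preceding step.
3. State whether a patient who stops ascorbate after a titration event leaves all protocol treatment or may continue olaparib. Stopping ascorbate alone is not the consequence that Section 8.2.1 now describes, so this is a choice for the sponsor and not a mere clarification.

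The cost is a few sentences in an amendment and one line in the pharmacy worksheet of Section 10.1.4, with no new procedures. The downside is lower or no ascorbate exposure in a few patients.

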## 8.2.2 Olaparib Dose Modifications

8.2.2.1 Dose Modifications for co-administration of strong or moderate CYP3A inhibitors or inducers, if co-administration becomes necessary during the study

It is recommended that known strong CYP3A inhibitors (eg, itraconazole, telithromycin, clarithromycin, boosted protease inhibitors, indinavir, saquinavir, nelfinavir, boceprevir, telaprevir) or moderate CYP3A inhibitors (ciprofloxacin, erythromycin, diltiazem, fluconazole, verapamil) should not be taken with olaparib. If there is no suitable alternative concomitant medication, then the patient should discontinue protocol treatment.

8.2.2.2 Olaparib Dose Modifications for concurrent Renal Impairment

If subsequent to study entry and while still on study therapy, a patient's estimated CrCl falls below the threshold for study inclusion ( $\geq$ 51 mL/min), retesting should be performed promptly.

For patients who develop moderate renal impairment (CrCl < 50 mL/min), hold dose until recovery.

Olaparib has not been studied in patients with severe renal impairment (creatinine clearance  $\leq$ 30 mL/min) or end-stage renal disease; if patients develop severe impairment or end stage disease, it is recommended that olaparib be discontinued.

# 8.2.2.3 Olaparib Dose Modifications for Toxicities

Any toxicity observed during the course of the study could be managed by interruption of the dose of study treatment or dose reductions.

Patients who require an interruption in olaparib >4 weeks due to toxicity must discontinue all study therapy.

Olaparib can be dose reduced to 250mg twice daily as a first step and to 200mg twice daily as a second step with the exception of cases of CTCAE v5.0 grade 3 or 4 anemia when dose should be reduced to 200mg twice daily as first step. If the reduced dose of 200mg twice daily is not tolerable, no further dose reduction is allowed and all study treatment should be discontinued.

Once dose is reduced, escalation is not permitted.

For guidance on dose reductions for management of AEs (including renal impairment) refer to **Table 4 and Table 5**.

In case a dose reduction is necessary, the Study treatment will be administered as follows:

Table 4 Dose reductions for study treatment to manage adverse events

Initial Dose	Following re-challenge post interruption: Dose reduction 1	Dose reduction 2
300 mg twice daily	250 mg twice daily	200 mg twice daily

Table 5 Dose reduction for study treatment if patient develops moderate renal impairment

Initial Dose	Moderate renal impairment (calculated creatinine clearance by Cockcroft -Gault equation or based on a 24 hour urine test between 31 and 50 ml/min): Dose reduction
300 mg twice daily	200 mg twice daily

Table 6 Dose reductions for study treatment if patient has to start taking a strong or moderate CYP3A inhibitor

Initial Dose	Moderate CYP3A inhibitor	Strong CYP3A inhibitor		
300 mg twice daily	150 mg twice daily	100 mg twice daily		

For guidance on dose reductions when concomitant strong or moderate CYP3A inhibitors cannot be avoided refer to **Table 6**.

When dose reduction is necessary patients will take one 150 mg tablet and one 100 mg tablet twice daily or two x 100 mg tablet twice daily or one 150 mg tablet twice daily or one 100 mg tablet twice daily.

Management of hematological toxicity

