# 7.6.1 Olaparib Administration

Patients will be administered olaparib twice daily at 300mg continually. Two 150mg olaparib tablets should be taken twice daily at the same time each day, approximately 12 hours apart with one glass of water. The olaparib tablets should be swallowed whole and not chewed, crushed, dissolved, or divided. Olaparib tablets can be taken with or without food.

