#### **Restricted concomitant medications**

Medications prohibited 6 months prior to enrollment

5-alpha reductase inhibitors are allowed if subject has been taking stable dose of medication for prior 6 months.

Strong or moderate CYP3A inhibitors

Known strong CYP3A inhibitors (e.g. itraconazole, telithromycin, clarithromycin, boosted protease inhibitors, indinavir, saquinavir, nelfinavir, boceprevir, telaprevir) or moderate CYP3A inhibitors (ciprofloxacin, erythromycin, diltiazem, fluconazole, verapamil) should not be taken with olaparib. See this link for a complete list of known CYP3A inhibitors: https://www.fda.gov/drugs/drug-interactions-labeling/drug-development-and-drug-interactions-table-substrates-inhibitors-and-inducers. During the study, if co-administration or a strong or moderate inhibitor is required because there is no suitable alternative medication, dose of olaparib should be reduced for the period of concomitant administration.

- Strong CYP3A inhibitors reduce the dose of olaparib to 100 mg twice daily for the duration of concomitant therapy with the strong inhibitor and for 5 half-lives afterwards.
- Moderate CYP3A inhibitors reduce the dose of olaparib to 150 mg twice daily for the duration of concomitant therapy with the moderate inhibitor and for 3 half-lives afterwards.
- After the washout of the inhibitor is complete, the olaparib dose can be re-escalated.

Strong or moderate CYP3A inducers

Strong (e.g. phenobarbital, phenytoin, rifampicin, rifabutin, rifapentine, carbamazepine, nevirapine, enzalutamide and St. John's Wort) and moderate (e.g. bosentan, efavirenz, modafinil) CYP3A inducers should not be taken with olaparib. See this link for a complete list of known CYP3A inhibitors: https://www.fda.gov/drugs/drug-interactions-labeling/drug-development-and-drug-interactions-table-substrates-inhibitors-and-inducers.

Effect of olaparib on other drugs

Based on limited in vitro data, olaparib may increase the exposure to substrates of CYP3A4, BCRP, OATP1B1, OCT1, OCT2, OAT3, MATE1 and MATE2K.

Based on limited in vitro data, olaparib may reduce the exposure to substrates of 2B6 (and potentially substrates of CYP2C9, CYP2C19 and P-gp).

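### Sections 7.7, 8.2.2.1 and 8.2.2.3 give three incompatible olaparib instructions for a man who needs a strong or moderate CYP3A inhibitor on study

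*Combined protocol and SAP*

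**What the plan says.** The regimen in Section 7.6.1 is "Patients will be administered olaparib twice daily at 300mg continually". Section 5.2 excludes men taking strong or moderate CYP3A inhibitors at entry, so the question arises only when one becomes unavoidable on study. Three places deal with that case.

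- **Section 7.7, restricted concomitant medications.** For strong inhibitors: "Strong CYP3A inhibitors reduce the dose of olaparib to 100 mg twice daily for the duration of concomitant therapy with the strong inhibitor". This reduction is kept up a further 5 half-lives. For moderate inhibitors: "Moderate CYP3A inhibitors reduce the dose of olaparib to 150 mg twice daily for the duration of concomitant therapy with the moderate inhibitor". This one is kept up a further 3 half-lives. Then: "After the washout of the inhibitor is complete, the olaparib dose can be re-escalated".
- **Section 8.2.2.3, olaparib modifications for toxicities.** After the toxicity steps (250 mg, then 200 mg) comes the sentence "Once dose is reduced, escalation is not permitted". Further down the same section is "Table 6 Dose reductions for study treatment if patient has to start taking a strong or moderate CYP3A inhibitor", giving 150 mg (moderate) and 100 mg (strong) from a 300 mg start.
- **Section 8.2.2.1, co-administration of CYP3A inhibitors or inducers.** Where the inhibitor has no acceptable substitute, the man is to come off protocol treatment.

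No section cross-refers to another on this point or says which takes precedence.

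**The concern.** The trigger is the same in all three places: an inhibitor that cannot be avoided. The instructions differ both on whether olaparib continues and, if it does, on whether the dose may go back up once the inhibitor has gone.

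Sections 3.0, 7.6 and 10.2.7 send sites to Section 8.2 for dose changes. A site that follows those pointers finds the CYP3A reductions and the no-escalation sentence together. The permission to re-escalate appears only in the concomitant-medication section. The trial is multi-center, so two sites could treat the same situation differently, each following written text.

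What is at stake is consistency of exposure. The primary endpoint is a PSA50 proportion in 12 patients assessed for 6 months. Men handled in three different ways could enter the same proportion, which would make a non-response harder to attribute to the planned regimen.

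**Working it through.** **1. The three rules side by side.**

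| Section | While the inhibitor is taken | After washout |
|---|---|---|
| 7.7 | 100 mg (strong) or 150 mg (moderate) twice daily, plus 5 or 3 half-lives | Re-escalation allowed; dose to return to not named |
| 8.2.2.3 | Same doses (Table 6), no duration given | Escalation barred, no exception stated |
| 8.2.2.1 | Off protocol treatment | Does not arise |

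Sections 7.7 and 8.2.2.3 agree on the lowered dose and, read literally, disagree on what follows. Section 8.2.2.1 disagrees with both, because they provide for continued treatment. Settling only the return to dose would leave the question of stopping open.

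**2. Does the no-escalation sentence reach Table 6?** For: it has no qualifier, and Table 6 is in the same section, together with Table 5 on renal impairment, so the section is not confined to toxicity. Against: the section heading refers to toxicities, and the sentence directly follows the toxicity steps. The wording supports either reading.

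**3. Size of the dose difference.** Inputs: 300 mg (Section 7.6.1), 150 mg and 100 mg (Section 7.7 and Table 6).

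- Strong inhibitor: 100/300 = 33% of the starting dose.
- Moderate inhibitor: 150/300 = 50%.

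**4. The plan's own design figures.** Inputs from Section 13.5: N = 12, success at 2 or more responders, null 3%, target 23%. The probability of 2 or more responders is 1 − (1−p)^12 − 12p(1−p)^11.

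- p = 0.03: exact type I error 0.0486, within the stated 0.05.
- p = 0.23: exact power 0.8009, matching the stated 80%.

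These figures do not depend on the inhibitor rules and stand as stated.

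**5. Scale, as illustration only.** One patient is 1/12 = 8.3 percentage points of the PSA50 rate. Suppose, with no support in the documents, that k of the 12 men respond at 3% instead of 23%. With a = 12 − k, power = 1 − 0.77^a·0.97^k − [a·0.23·0.77^(a−1)·0.97^k + k·0.03·0.97^(k−1)·0.77^a].

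- k = 0: 80.1%
- k = 1: 76.4%
- k = 2: 72.1%
- k = 3: 67.2%

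Neither k nor the 3% response rate for such men is given in the plan, so this is not an estimate of the effect.

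**The case against.** The strongest reply is that the text can be read in harmony. The no-escalation sentence belongs to a toxicity section, while Section 7.7 is specific to inhibitors and is the only place that gives a duration. A site using Table 6 would need Section 7.7 to know how long the reduction lasts, and would find the permission to re-escalate there. This is plausible and may be the intent. It still has to be inferred, and it does nothing about Section 8.2.2.1. Inhibitors are also discouraged on study, so the case may be uncommon; the documents give no frequency either way.

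Several stronger readings are tempting but not supported.

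- A reader might infer that Section 8 as a whole keeps the man on the lowered dose until progression. Section 8.2.2.1, the subsection written for CYP3A co-administration, stops treatment instead.
- A reader might see a second conflict between Table 6 and the 200 mg step. That sentence, "If the reduced dose of 200mg twice daily is not tolerable, no further dose reduction is allowed and all study treatment should be discontinued", depends on tolerability and ends the toxicity ladder. The same section gives tablet instructions for 150 mg and 100 mg, so it expects doses below 200 mg.
- A reader might call the lowered dose after washout under-dosing. The documents do not say so, and that is a clinical judgement.
- A reader might think the reasons for reductions go unrecorded. Section 8.2.2.3, under interruptions for non-toxicity events, already requires them in the eCRF.

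**Conclusion.** The conflict is real and three-way. For the same clinical situation, a man could stop protocol treatment, stay at 33% to 50% of the starting dose after the inhibitor has gone, or be re-escalated. The middle outcome rests on the literal reading of the no-escalation sentence; a toxicity-only reading is open but unstated.

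A reader might go further and infer a definite loss of power or a set number of weeks on a lowered dose. The documents do not support that: they give neither the frequency nor the timing of inhibitor use, nor any response rate at lowered doses. The effect on the PSA50 result cannot be quantified, and the sample size and power in Section 13.5 are unaffected. This is an inconsistency of wording that can change what patients receive. It is not a fault in the design calculation.

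**What to change.** Reconcile Sections 7.7, 8.2.2.1 and 8.2.2.3, including Table 6, so that one rule applies throughout when a strong or moderate CYP3A inhibitor cannot be avoided. State in Section 8.2.2.3 whether the no-escalation sentence covers the Table 6 reductions or only those made for toxicity. If the dose may go back up, say to which level, since Section 7.7 does not. The clinical team decides which rule applies. The cost is about one sentence in each of the three sections, with no change to sample size, endpoint or data collection.
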